#### Adverse Events of Special Interest

AESIs will be reported separately but in the same way as SAEs.

#### Solicited Local AEs

Solicited local AEs will be summarized by PT after each vaccination visit, and broken down by maximum intensity.

In addition, the incidence will be calculated by severity (i.e. the number of subjects developing a particular local solicited AE during the 8-day period after each vaccination divided by the number of subjects actually receiving this vaccination) with corresponding 95% Clopper-Pearson CI. The incidence will also be calculated for any solicited local AE for each vaccination period and per subject.

The duration of the AEs will be included in the listing. The duration of the AEs will also be summarized using the mean, SD, median, minimum and maximum.

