### **8.1.2.2 Solicited AEs**

Within this clinical trial protocol solicited AEs are defined as all symptoms specifically listed in the memory aid provided to the subjects following each vaccination. The subjects are requested to monitor and record local symptoms (i.e. erythema, swelling, induration, pruritus and pain at the injection site) as well as general symptoms (i.e. body temperature, headache, chills, myalgia, nausea and fatigue) in the memory aid daily for the day of vaccination and the following seven days (Days 0-7, 8 day period).

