### 3.2 Analysis Populations

#### 3.2.1 Full Analysis Set (FAS)

This is the subset of subjects who received at least one injection and for whom any data are available.

The main analysis of safety will be performed on this analysis set.

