### 3.3 Definitions, Data Conventions and Handling of Missing Data

#### 3.3.1 Missing Data

No imputation of missing titers will be performed.

For the analysis of safety data incomplete AE and medication start and end dates will be imputed in order to assign these events to the correct vaccination period.

Missing Vital Signs data for Visit 1 will be imputed using screening (or latest re-screening) values. However, this will be displayed as 'Baseline' values in the tables and listing for Vital Signs data without reference to whether the data originated from Visit 1 or SCR.

For prior and concomitant medication and AEs imputation of partial start and end dates will be done for analysis purpose according to the following rules:

Missing	Rule for start date	Rule for end date	Flag for imputation
Day	First of month*	Last of month*	D
Month †	1. January*	31. December*	M
Year †	no imputation	Last visit date	Y

\* Unless the imputed start date is before first visit date, in which case first visit date is used; or the imputed end date is after last visit date in which case last visit date available is used.

† It is assumed that a missing month implies a missing day as well, and that a missing year implies a missing month and day.

All data will be listed and summarized as captured in the eCRF. All listings will display the original dates as captured in the eCRF.

If the imputation of a partial start date of an AE leads to a start date prior to the date of first vaccination, it will be set to the date of first vaccination following the worst case principle.

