#### Solicited local AEs reported in the subject memory aid (on days of vaccination and during the following seven days)

- Injection Site Erythema (Redness)

- Injection Site Swelling
- Injection Site Pain
- Injection Site Induration
- Injection Site Pruritus (Itching)

Solicited general AEs reported in the subject memory aid (on days of vaccination and during the following seven days)

- Body Temperature (Fever)
- Headache
- Myalgia (Muscle pain)
- Chills
- Nausea
- Fatigue

Unsolicited AEs reported (on days of vaccination and during the following 28 days)

- Other, unsolicited local and general adverse events following vaccination

SAEs

AESIs

In case an AESI is also an SAE it will be treated and reported as an SAE.

Prior and Concomitant medication

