### **3.5.7 Compliance**

Compliance will be evaluated with respect to the number vaccinations received and the number of memory aids completed.

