#### Solicited General AEs

Solicited general AEs will be summarized in the same manner as solicited local AEs.

In addition a similar summary table will be produced for relationship of the AEs to trial vaccine. Also the incidences of AEs with reasonable possibility of vaccine contribution (i.e. relationship to vaccine documented as “possible”, “probable”, “definite” or missing), and those with Grade  $\geq 3$  and with reasonable possibility of vaccine contribution will be summarized per vaccination period and overall by subject.

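### Solicited-reaction incidence is divided by everyone vaccinated, so any vaccination without memory-aid data can only lower the reported rate

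*SAP*

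**What the plan says.** - **Denominator.** SAP 3.5.9, Solicited Local AEs, takes the subjects with a given reaction in the 8-day period "divided by the number of subjects actually receiving this vaccination", with a 95% Clopper-Pearson interval. It also asks for incidence per vaccination period and per subject. For general reactions: "Solicited general AEs will be summarized in the same manner as solicited local AEs".
- **Numerator.** In Protocol 8.1.2.2, "solicited AEs are defined as all symptoms specifically listed in the memory aid provided to the subjects following each vaccination". Protocol 8.2.6 has the investigator collect this information and transfer it to the eCRF. SAP 3.4.2 describes the variable as "Solicited local AEs reported in the subject memory aid", with parallel wording for general reactions.
- **Analysis set.** The safety tables use the FAS, meaning subjects who "received at least one injection and for whom any data are available". A returned aid is not required.
- **Missing data.** SAP 3.3.1 opens with "No imputation of missing titers will be performed" and goes on to partial AE and medication dates and Visit 1 vital signs. It does not mention memory aids. The valid-case rule in Protocol 9.3 covers immunogenicity variables only.
- **Compliance.** SAP 3.5.7: "Compliance will be evaluated with respect to the number vaccinations received and the number of memory aids completed". The index in SAP 5.1 has one compliance table (15.1.5.1), on vaccinations received. The compliance listings in SAP 5.2 cover visit and sampling dates and product administration.

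**The concern.** Numerator and denominator rest on different groups of people. The numerator can count only reactions that were recorded, mainly on the memory aid. The denominator counts everyone injected. A subject who loses the aid, returns it blank, or leaves before the collection visit (Visit 2, 4 or 7) is still in the denominator, and the arithmetic treats that vaccination as free of reactions.

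Occurrence of solicited local reactions and of solicited general reactions are two named secondary endpoints. They bear on whether doubling the dose or adding a booster is tolerated as well as the standard regimen. If return differs between groups, part of the difference shown between regimens would reflect diary return. Protocol 2.6.3 already raises possible under-reporting as a partial explanation for lower local reaction rates in HIV-infected subjects, so a rule that can err only downward is unhelpful here. Because the SAP plans to count completed aids, its authors anticipated incomplete return, but that count enters no rate.

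**Working it through.** **Inputs from the documents.** 30 subjects per group (Protocol 9.2, SAP 3.1); denominator is all who received the vaccination (SAP 3.5.9); 95% Clopper-Pearson intervals.

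**Inputs assumed.** The documents give neither a return rate nor an expected reaction rate. Take a true incidence p = 60%; m = 0, 1, 3 or 6 of 30 aids missing; non-return unrelated to reaction; and no capture by another route.

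**The plan's own figure first.** SAP 3.1 states at least 95% probability of seeing an AE of incidence 1 in 10 with 30 subjects. 1 − 0.9^30 = 0.9576, so it reproduces. For a reaction seen only through the aid, the exponent is the number of aids with data: 95.3% with 29, 94.8% with 28, 94.2% with 27, 92.0% with 24. The statement therefore holds for such reactions with at most one aid missing per group.

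**Expected reported rate.** E = p × (30 − m)/30, a relative understatement of m/30. Coverage is the probability that the nominal 95% interval contains p when reactors among returned aids are binomial with size 30 − m.

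| Aids missing | Relative understatement | Expected rate, denominator 30 | Coverage, denominator 30 | Coverage, returned aids |
|---|---|---|---|---|
| 0 | 0% | 60% | 96.2% | 96.2% |
| 1 | 3.3% | 58% | 95.9% | 96.3% |
| 3 | 10% | 54% | 92.5% | 97.1% |
| 6 | 20% | 48% | 78.7% | 96.5% |

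The loss of coverage depends on p. At a true 10% the interval over 30 does not under-cover (99.2% with none missing, 99.8% with 6 missing). At a true 80% with 6 missing, coverage is 65.6%.

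**Worked examples.**
- 3 missing, 16 reactors: 16/30 = 53.3% (34.3 to 71.7%) as written; 16/27 = 59.3% (38.8 to 77.6%) among those with data. Counting the missing as all non-reactors or all reactors gives bounds of 16/30 = 53.3% and 19/30 = 63.3%.
- 6 missing, 14 reactors: 14/30 = 46.7% (28.3 to 65.7%) against 14/24 = 58.3% (36.6 to 77.9%). Bounds 46.7% and 20/30 = 66.7%.
- 6 missing, no reactors: the upper limit is 11.6% for 0/30 and 14.2% for 0/24.

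**Unequal return.** One group returns 30/30, another 24/30, both with true 60%: 60% − 60% × 24/30 = 12 points of difference that is not real. For scale, the sampling half-width for two groups of 30 at 60% is 1.96 × √(2 × 0.6 × 0.4/30) = 1.96 × 0.126, about 25 points. The distortion is smaller than the noise, but it is systematic.

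**The case against.** **No rule scores a missing aid as no reaction.** A reader might infer that the SAP contains one. It does not; that is the arithmetic consequence of the denominator, and only where nothing else records the reaction. Other routes exist: immediate AEs are recorded after each injection, the injection site is examined at Visits 2, 4 and 7, subjects are asked about AEs at each active-phase visit, the aid is reviewed with the subject on collection, and a concluding safety visit is attempted for those who leave. Protocol 8.1.2.2 defines a solicited AE by its being listed on the aid, so an orally reported Day 2 headache might be counted. SAP 3.4.2 points the other way. This stands: the text is ambiguous, and other routes may shrink the shortfall. Nothing ensures that they remove it.

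**The alternative is not assumption-free.** If reactors return their aids more readily, the rate among returned aids is too high. This also stands. The all-vaccinated rate is a valid lower bound and should be kept.

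**Group 3 and its third aid.** One might argue that Group 3 is understated more because it has one more aid to lose. The documents do not support this. Per-vaccination rates use each vaccination's own denominator, and Groups 1 and 2 have no third vaccination. Per subject, a third aid is a further chance to enter the numerator.

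**Importance.** One might read these rates as the main test of tolerability. The primary endpoint is serious and/or unexpected AEs, the comparisons are descriptive, and no decision threshold depends on solicited rates.

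**Partly handled.** SAP 3.5.7 commits to evaluating completed aids, and a missing index entry does not cancel that. But the commitment does not change the rate.

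**Conclusion.** The concern holds within limits. As written, the reported incidence of a solicited reaction cannot exceed the true proportion among those vaccinated, and falls below it whenever a reactor's data are missing and no other route captures the reaction. If non-return is unrelated to reaction, the expected rate is the true rate times the return fraction: 3.3%, 10% or 20% too low in relative terms with 1, 3 or 6 of 30 aids missing. The return rates are assumptions. With complete return there is no error, so the documents do not support a statement that reactogenicity in this trial is understated. They support the narrower conclusion that the plan would understate it if aids were missing, and that the indexed outputs would not let a reader see by how much. The effect is confined to the solicited secondary endpoints. The change is worth making because it replaces a stated rule at little cost.

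**What to change.** In SAP 3.5.9, for solicited local and general AEs:

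1. Main denominator per vaccination: subjects who received it and have solicited data for that symptom on at least one of Days 0 to 7, or a solicited reaction recorded by another route. Count the latter separately, since they enter only because they reacted.
2. Per-subject denominator: subjects with such data after at least one vaccination.
3. Show the numbers vaccinated and with memory-aid data by group and vaccination.
4. Index the memory-aid compliance table that SAP 3.5.7 implies.
5. Keep the all-vaccinated rate as a sensitivity analysis (lower bound), with an upper bound that counts missing aids as reactions.
6. State that the main rate assumes non-return is unrelated to reaction.
7. Leave all vaccinated subjects as the denominator for unsolicited AEs, SAEs and AESIs.

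Cost: SAP wording, extra columns and one table, with no new data collection. Denominators are slightly smaller and intervals wider. A partly completed aid still counts its blank days as reaction-free, which a table footnote should say.

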#### Solicited General AEs

Solicited general AEs will be summarized in the same manner as solicited local AEs.

In addition a similar summary table will be produced for relationship of the AEs to trial vaccine. Also the incidences of AEs with reasonable possibility of vaccine contribution (i.e. relationship to vaccine documented as “possible”, “probable”, “definite” or missing), and those with Grade  $\geq 3$  and with reasonable possibility of vaccine contribution will be summarized per vaccination period and overall by subject.

#### Unsolicited AEs

Treatment emergent unsolicited AEs will be summarized by SOC and PT and vaccination period and by subject.

A summary of the number of AEs by intensity and by relationship to trial vaccination will also be presented.

The number of AEs with a reasonable possibility of being related to the vaccine will be presented in a separate listing and summarized in a table by SOC and PT and vaccination period and by subject.

Non-treatment emergent AEs will only be flagged and included in the listing, but will not be included in the tables.

### **3.5.10 Clinical Laboratory Variables (Hematology, Chemistry, HIV)**

All measured hematology and chemistry values (and changes from baseline for continuous parameters) will be listed and summarized per visit using descriptive statistics.

Summary tables will be produced for the number of high and low laboratory values per visit by hematology and chemistry parameters.

In addition, all clinical laboratory values outside the normal range will be listed with screening number, demographic information and flagging of abnormal values (L=Below normal range, H=Above normal range) with their clinical significance.

‘Shift tables’ will be used to evaluate categorical changes from SCR to Visit 2 and SCR to Visit 4 (and SCR to Visit 7 in Group 3) with respect to normal ranges (below, within, above normal range) in hematology and chemistry parameters.

Measured CD4 count and viral load values and changes from Baseline will be summarized per visit using descriptive statistics. A plot of median CD4 counts per visit and per treatment group will be produced. All measured values will be listed.

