- described and details on how and when the subject was diagnosed are documented in the subjects source data/medical records by a current or previous physician or the PI, this is sufficient and the subject can be enrolled in the trial.
3. On stable antiretroviral therapy (ART) i.e. Combination ART for at least three months prior to screening visit in this clinical trial with no change to the therapy during these three months.
  4. Screening HIV-1 RNA < 200 copies/ml
  5. Screening CD4 counts  $\geq 100$  cells/ $\mu$ l and  $\leq 500$  cells/ $\mu$ l.
  6. Documented nadir CD4 count < 200 cells/ $\mu$ l at any time prior to screening visit. If nadir is not documented lowest documented CD4 count < 200 cells/ $\mu$ l at any time prior to screening visit.
  7. Hemoglobin  $\geq 9.0$  g/dl for female subjects,  $\geq 10.0$  g/dl for male subjects.
  8. Platelets  $\geq 100,000/\text{mm}^3$ .
  9. Ability and willingness of subject to provide written informed consent.
  10. Body Mass Index (BMI)  $\geq 18.5$  and < 35 kg/m^2.
  11. Women of childbearing potential (WOCBP) must have used an acceptable method of contraception for 30 days prior to the first vaccination, must agree to use an acceptable method of contraception during the trial, and must avoid becoming pregnant for at least 28 days after the last vaccination. A woman is considered of childbearing potential unless post-menopausal (defined as  $\geq 12$  months without a menstrual period) or surgically sterilized. Acceptable contraception methods are restricted to abstinence, barrier contraceptives, intrauterine contraceptive devices or licensed hormonal products.
  12. WOCBP must have a negative serum pregnancy test at screening (SCR) and a negative urine pregnancy test within 24 hours prior to each vaccination.
  13. Absolute neutrophil cell count  $\geq 750/\text{mm}^3$ .
  14. Adequate renal function defined as a calculated Creatinine Clearance (CrCl) > 60 ml/min as estimated by the Cockcroft-Gault equation.
    - a) For men:  $(140 - \text{age in years}) \times (\text{body weight in kg}) \div (\text{serum creatinine in mg/dl} \times 72) = \text{CrCl (ml/min)}$
    - b) For women: multiply the result for men by 0.85 = CrCl (ml/min).

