##### 8.1.2.1 Unsolicited AEs

Unsolicited AEs are defined as any untoward (undesirable) occurrence of a medical event in a clinical trial subject temporally associated with the administration of an IMP or a medical product (MP) which does not necessarily have a causal relationship with this IMP/MP. For Group 1 and 2 up to Visit 5 (Week 8) and for Group 3 up to Visit 8 (Week 16) all AEs (e.g. feeling of ill-health, subjective symptoms and objective signs, intercurrent diseases, accidents, etc.) observed by the investigator and/or reported by the subject must be recorded in the eCRF regardless of the assessment of causality in relationship with the IMP/MP.

Abnormal laboratory values assessed as being clinically significant by the investigator are to be documented as AEs. In addition, abnormal laboratory values fulfilling the Grade 3 or Grade 4 criterion according to the toxicity scale ([Section 16.1](#); [Appendix I: Toxicity Scale for Laboratory Values](#)) are to be documented as AE in the eCRF, regardless of whether they are considered clinically relevant or not. For lab values fulfilling the Grade 3 or 4 criterion, the decision to repeat the labs is left at the discretion of the PI. Toxicity grade and seriousness of an AE will be assessed separately, i.e. a Grade 3 or Grade 4 AE will not automatically be regarded as serious.

The investigator should ask the subject if they have experienced any AEs since their last visit. All intercurrent diseases reported by the subject, need to be recorded by the investigator in the appropriate section of the eCRF.

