## 8.2.8 Safety Laboratory Measurements

The intensity of laboratory / systemic quantitatively measured toxicities will be graded according to the toxicity scale in [Section 16.1; Appendix I: Toxicity Scale for Laboratory Values](#). These grading scales include the laboratory values determined with the routine safety parameters. In case of other laboratory values not included in the routine safety laboratory and not listed in [Section 16.1; Appendix I: Toxicity Scale for Laboratory Values](#), the [Division of AIDS Table for Grading the Severity of Adult and Pediatric Adverse Events, Version 1.0](#), December 2004, Clarification August 2009 will be used for grading of laboratory toxicities.

Safety laboratory is determined at SCR, Visit 2, Visit 4, Visit 7 (Group 3 only) and at any other visit(s) if clinically indicated. The safety laboratory measurements are performed at a central laboratory. Laboratory normal ranges are provided by the central laboratory and filed in the Investigator File. Safety laboratory parameters to be evaluated are:

Hematology: Red blood cell count, hemoglobin, total and differential White Blood Cell count (WBC), platelet count (Hematocrit, mean corpuscular/cell volume (MCV), mean corpuscular/cellular hemoglobin (MCH) , mean corpuscular hemoglobin concentration (MCHC) and red blood cell distribution width (RDW) are routinely performed as part of the complete blood cell count and will be included in the laboratory report).

HIV specific parameters: CD4 count will be determined with every safety laboratory and at Visit 8 and FU 1 and FU 2. Viral load will be determined at SCR and at Visit 2. Viral load will be determined at any other visit if clinically indicated.

Serum chemistry:

Total bilirubin, AP, AST, ALT, serum creatinine (for calculation of CrCl at SCR), sodium, potassium, calcium, troponin I (troponin mandatory at SCR and in addition Visit 2, Visit 4 and Visit 7 (Group 3 only)).

Pregnancy test:

A  $\beta$ -human choriongonadotropin (HCG) pregnancy test will be conducted for all WOCBP at SCR, within 24 hours prior to each vaccination and at the individual last active trial phase visit (i.e. Visits 1, 3, 5 and Visits 6 and 8 for Group 3 respectively). At SCR a serum  $\beta$ -HCG pregnancy test will be performed; all other pregnancy tests will be conducted as urine  $\beta$ -HCG tests.

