## **3.5 Analysis and Presentation Methods**

### **3.5.1 Listings and Descriptive Statistics**

All individual data entered in the eCRF and derived data will be listed as measured in the Individual Subject Data Listing.

For ELISA and PRNT titers descriptive statistics will be based on Geometric Means and confidence intervals (CI). Other, continuous measurements will be summarized by means of descriptive statistics (i.e. number of observations (N), mean, SD, minimum (Min), median, maximum (Max)) and categorical data will be summarized by means of frequency tables (i.e. count and percentages) and CI, if not stated otherwise.

All tables and listings will be sorted by scheduled visit (and subject, if appropriate).

All tables will be presented split by treatment groups (Groups 1 - 3).

Repeat assessments/measurements and unscheduled assessments/measurements will be included in the Individual Subject Data Listing. In case of any repeats of safety laboratory values, the repeat values will be used for the before-treatment assessment and the original value for the post-trial assessment. All other repeat values will be listed in a separate listing.

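### No planned table counts laboratory worsening by toxicity grade, so a Grade 1 to Grade 2 move within low or high is uncounted by group unless judged clinically significant

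*SAP*

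**What the plan says.** **Grading.** Protocol 8.2.8 states that quantitatively measured laboratory toxicities "will be graded according to the toxicity scale in" Appendix I, which gives the bands in Tables 6 and 7. Appendix I applies Grades 1 and 2 only to values outside the laboratory's normal range.

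**Adverse event rules.** Protocol 8.1.2.1 has two routes. A laboratory abnormality that the investigator considers clinically significant is an adverse event at any grade. In addition, "abnormal laboratory values fulfilling the Grade 3 or Grade 4 criterion according to the toxicity scale" are adverse events whether or not they are thought relevant.

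**Entry.** The inclusion criteria (protocol 1.5) admit abnormal values. Criterion 13, for example, sets a floor for "Absolute neutrophil cell count" of 750/mm3. Platelets may be as low as 100,000/mm3, AST, ALT and alkaline phosphatase as high as 2.5 x ULN, and bilirubin as high as 2 x ULN, with a further allowance for elevation due to atazanavir.

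**Analysis.** SAP 3.5.10 plans four kinds of output for hematology and chemistry:

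- measured values ("and changes from baseline for continuous parameters) will be listed and summarized per visit using descriptive statistics"), which under SAP 3.5.1 means N, mean, SD, minimum, median and maximum, by treatment group;
- high and low counts: "Summary tables will be produced for the number of high and low laboratory values per visit";
- shift tables from screening to Visits 2 and 4, and to Visit 7 in Group 3, "with respect to normal ranges (below, within, above normal range) in hematology and chemistry parameters";
- a listing in which "all clinical laboratory values outside the normal range will be listed with screening number, demographic information and flagging of abnormal values" as low or high, with clinical significance.

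The laboratory tables indexed in SAP 5.1 (15.3.3.1 to 15.3.3.7) are mean-value and shift tables. None is by toxicity grade.

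**The concern.** A three-level shift table works well when nearly everyone starts inside the normal range. Here entry admits people who start low or high. Once a subject is in an outer category, further worsening cannot move them to another cell, and the subject adds one to the high or low count both before and after.

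The primary objective is safety when the dose or the number of injections is increased. A natural question is whether more subjects worsen on laboratory measures in Group 2 or Group 3 than in Group 1. The protocol already has a fixed scale for answering it, and the planned tables do not use it. Below Grade 3, the only route from such a change to a per-group count is the investigator's judgement of clinical significance, made in an open-label trial. A grade is a fixed threshold applied alike in all groups.

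**Working it through.** The plan states no figure on this point, so there is none to reproduce. The check compares the entry limits with the toxicity bands, the adverse event rule and the planned tables, and then asks what the change summaries would show.

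**Step 1. Entry limits against bands** (protocol 1.5; Appendix I, Tables 6 and 7)

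| Parameter | Entry limit | Grade 1 | Grade 2 | Grade 3 |
|---|---|---|---|---|
| ALT, AST, alkaline phosphatase (x ULN) | at most 2.5 | 1.25 to 2.5 | 2.6 to 5.0 | 5.1 to 10 |
| Bilirubin (x ULN) | at most 2 | 1.1 to 1.5 | 1.6 to 2.5 | 2.6 to 5.0 |
| Platelets (/mm3) | at least 100,000 | 100,000 to 124,999 | 50,000 to 99,999 | 25,000 to 49,999 |
| Neutrophils (/mm3) | at least 750 | 1,000 to 1,300 | 750 to 999 | 500 to 749 |

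The limits for liver enzymes and platelets lie at the worse end of Grade 1. Those for bilirubin and neutrophils lie inside Grade 2.

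**Step 2. Moves that the shift table cannot show**

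- ALT 2.4 to 5.0 x ULN: Grade 1 to Grade 2, a factor of 5.0 / 2.4 = 2.1. The cell is high-to-high. Both values are multiples of the ULN above 1, so this needs no assumption about the normal range.
- Platelets 124,000 to 50,000: Grade 1 to Grade 2, a fall of 74,000 / 124,000 = 60%. The cell is low-to-low if 124,000 is below the laboratory's lower limit. The documents do not give that limit.

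Neither value reaches Grade 3, so neither is an automatic adverse event.

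**Step 3. Starting points where the gap closes.** A subject who enters at Grade 2 (neutrophils 750 to 999, or bilirubin 1.6 to 2.0 x ULN) has Grade 3 as the next step, and Grade 3 is recorded automatically. The uncounted grade change is therefore Grade 1 to Grade 2.

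**Step 4. What the change summaries would show.** As an illustration on assumed data, take 30 subjects in a group, of whom k go from 2.5 to 5.0 x ULN while the rest do not change. Mean change = 2.5k / 30.

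| k | Shift-table changes | Subjects up one grade | Mean change | Median change | Maximum change |
|---|---|---|---|---|---|
| 1 | 0 | 1 | 2.5 / 30 = 0.08 | 0 | 2.5 |
| 5 | 0 | 5 | 12.5 / 30 = 0.42 | 0 | 2.5 |
| 10 | 0 | 10 | 25 / 30 = 0.83 | 0 | 2.5 |

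The maximum shows that somebody worsened but is the same for one subject and for ten. The median does not move. The mean does move, but it mixes the number of subjects with the size of the change, and real data would add variation in the other subjects. None of these is a count of subjects who worsened.

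**The case against.** The case against is substantial, and most of it stands.

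- **The SAP does what the protocol asks.** Protocol 9.4.2 calls for marking results against the reference range and counting those outside it. The SAP does this and adds shift tables. No passage promises a table by grade. A reader might infer a contradiction between the two documents, but there is none: the protocol uses grades to document adverse events and in the halting rules.
- **Worsening is not invisible.** A reader might infer this from the shift table alone. The change summaries carry the extremes by group, all values are listed, and out-of-range values are listed again with clinical significance. Thirty subjects per group can be reviewed by eye.
- **A change below Grade 3 can be an adverse event.** It would be wrong to read 8.1.2.1 as requiring only Grade 3 and 4 values to be recorded. A clinically significant value of any grade is an adverse event and, if treatment emergent, enters the tables by system organ class, preferred term, intensity and relationship.
- **No endpoint counts Grade 1 or 2 laboratory changes.** The primary endpoint concerns serious or unexpected events, and the graded secondary endpoint concerns related Grade 3 or 4 events.
- **Some examples need the laboratory's limits.** The platelet case depends on a lower limit of normal that is not in the documents. A neutrophil case would as well.

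What these points leave open is the group-level count. A listing identifies individuals without comparing groups, an extreme value does not count subjects, and the adverse event route below Grade 3 rests on judgement by investigators who know the assignment.

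**Conclusion.** The point holds as a modest improvement. The SAP plans no tabulation of laboratory toxicity grade or grade shift. Grade 1 to Grade 2 worsening within an already low or high category, when not judged clinically significant, is not counted by group in any planned table. It can be seen only indirectly in the change summaries and per subject in the listings.

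The practical size cannot be given, because the number of subjects who start at Grade 1 is not stated. It could be none or many. What can be said is that a change as large as a doubling of ALT, from 2.5 to 5.0 x ULN, leaves the shift table unchanged.

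The conclusion does not depend on the platelet example, since the ALT example needs no laboratory limit. It does not support saying that safety signals would be missed, that Grade 3 or 4 values escape capture, or that the SAP departs from the protocol. No endpoint, error rate or sample size is affected.

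**What to change.** In SAP 3.5.10, add a shift table by treatment group for hematology and one for chemistry: Appendix I grade at screening against grade at Visit 2 and at Visit 4, with Visit 7 shown separately for Group 3. Give the number and percentage of subjects rising by one or more grades at each visit, among those with both values. If a worst-grade column is shown, restrict the comparison between groups to Visits 2 and 4, because Group 3 has an extra laboratory visit and so one more chance to show a high grade.

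Three details belong in the derivation:

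- Grade high and low directions separately where Tables 6 and 7 do so (sodium, potassium, calcium, white cells).
- Apply the Appendix I rule that Grades 1 and 2 require a value outside the normal range.
- State a rounding rule for values that fall between printed bands, such as 2.55 x ULN.

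The cost is one derived variable and one table per panel, plus entries in SAP 5.1. The data are already collected, and trial procedures do not change. It is better done before database lock, because the SAP's opening section requires any analysis added later to be flagged as unplanned.
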